### 11.2.20 Pharmacokinetics Concentrations Data

The dataset contains the information from the Pharmacokinetics Concentration (PC) and its supplemental domain, in a basic data structure.

**Analysis value** is defined as the value at the visit (numeric result in standard units). Original results recorded as below the lower limit of quantification (LLOQ) are set to zero.

**Analysis Relative Time** is defined, for Visits 3 to 5, as the amount of time between the PK sample and the next study drug intake, expressed in minutes (**Analysis Relative Time Unit** is defined as 'MINUTES').

**Analysis Relative Day** is defined, for Visits 3 to 7, as the number of days elapsed between the last dose and the PK sampling.

In addition to the **Analysis Record Flag** populated as described in the general section, a second **Analysis Record Flag** is created to identify samples taken under the expected conditions i.e.,

- For analysis of Visits 3 to 5: samples taken before the morning dose and one day after the last dose
- For analysis visits Week 12 and EOT: samples taken within 1 to 7 days following the last dose.

#### 11.2.21 Physical examination data

The dataset contains the information from the Physical Examination (PE) and its supplemental domain, in a basic data structure. No derivations are needed.

#### 11.2.22 Childbearing potential data, contraception, and pregnancy test data

This dataset contains the information from the Reproductive System Findings (RP) domain together with the results of the pregnancy tests recorded in LB domain.

### 12 HANDLING OF MISSING/INCOMPLETE DATE AND TIME FIELDS

This section describes some general principles to be followed in the case of missing or incomplete dates/times. Missing parts for specific dates/times are changed into acceptable non-missing values as described in the below [Table 15](#).

**Table 15** Handling of missing date and time

| Type of date/time                                      | Imputation method when date/time is incomplete   | Imputation method when date/time is missing |
|--|--|---|
| Start of study treatment
(Randomized subjects only) | Day is missing (i.e., "yyyy.mm")
Whichever is the later of "yyyy mm.01" or the date of randomization
Day and month are missing (i.e., "yyyy")
Whichever is the later of "yyyy.01.01" or the date of randomization | Date of randomization (IVRS)                |
| End of study treatment
(Randomized subjects only)   | Day is missing (i.e., "yyyy.mm")
Whichever is the earlier of "yyyy mm.28/29/30/31" and the Visit 6 (EOT) date  | Date of V6 - (Premature) End of Treatment   |

| Type of date/time  | Imputation method when date/time is incomplete  | Imputation method when date/time is missing                       |
|--|---|---|
| Start Date of Adverse Event
(Randomized subjects only) | 
Day and month are missing (i.e., "yyyy")
                     Whichever is the earlier of "yyyy.12.31" and the Visit 6 (EOT) date
 
Day is missing (i.e., "yyyy.mm")
                     If month and year of the episode = month and year of first study treatment intake then
                         Start date=date of first study treatment intake,
                         otherwise
                         Start date= yyyy.mm.01
 
Day and month are missing (i.e., "yyyy")
                     If year of the episode = year of first study treatment intake then
                         Start date = date of first study treatment intake,
                         otherwise
                         Start date= yyyy.01.01
 | Date of first study treatment intake                              |
| End Date of Adverse Event
(Randomized subjects only)   | 
Day is missing (i.e., "yyyy.mm")
                     If the year and the month are the same as the year and the month of last visit then
                         End date= Last visit date,
                         otherwise
                         End date=yyyy.mm.28 or 29 or 30 or 31
 
Day and month are missing (i.e., "yyyy")
                     If the year is the same as the year of last visit then
                         End date= Last visit date,
                         otherwise
                         End date=yyyy.12.31
  | No approximation, the AE is considered as ongoing in the analysis |
| Date of first SLE symptoms                                       | 
Day is missing (i.e., "yyyy.mm")
                     If the year and the month are the same as the year and the month of screening then
                         Start date= Screening date,
                         otherwise
                         Start date=yyyy.mm.01
 
Day and month are missing (i.e., "yyyy")
                     If the year is the same as the year of screening then
                         Start date= Screening date,
                         otherwise
                         Start date=yyyy.01.01
  | Date of V1 - Screening  |

| Type of date/time        | Imputation method when date/time is incomplete   | Imputation method when date/time is missing                               |
|--------------------------|--|---|
| Date of SLE diagnosis    | 
Day is missing (i.e., “yyyy.mm”)
If the year and the month are the same as the year and the month of screening then
Start date= Screening date,
otherwise
Start date=yyyy.mm.01
 
Day and month are missing (i.e., “yyyy”)
If the year is the same as the year of screening then
Start date= Screening date,
otherwise
Start date=yyyy.01.01
               | Date of V1- Screening   |
| Start Date of Medication | 
Day is missing (i.e., “yyyy.mm”)
If the year and the month are the same as the year and the month of screening then
Start date= Screening date,
otherwise
Start date=yyyy.mm.01
 
Day and month are missing (i.e., “yyyy”)
If the year is the same as the year of screening then
Start date= Screening date,
otherwise
Start date=yyyy.01.01
               | Date of V1- Screening   |
| End Date of Medication   | 
Day is missing (i.e., “yyyy.mm”)
If the year and the month are the same as the year and the month of last visit then
End date= Last visit date,
otherwise
End date=yyyy.mm.28 or 29 or 30 or 31
 
Day and month are missing (i.e., “yyyy”)
If the year is the same as the year of last visit then
End date= Last visit date,
otherwise
End date=yyyy.12.31
 | No approximation, the medication is considered as ongoing in the analysis |

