### ***3.1.1.2 Treatment period***

The treatment period will last 12 weeks. Visits during the treatment period will include the post-randomization assessments of the Randomization visit and visits at Weeks 2, 4, 8, 12.

The End-of-Treatment (EOT) visit will take place at Week 12 or earlier in case of premature permanent discontinuation of study treatment. In all cases, the EOT visit should take place 1 day after the last dose of study treatment intake but no later than 7 days after the last dose of study treatment intake.

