### **7.3.2 Pharmacokinetic assessments**

PK samples will be collected pre-dose (except EOT and EOS) at all visits from Visit 3 (Week 2) to Visit 7 (EOS).

The date and the time of blood sample collection will be entered in the eCRF. The date and time of the last study treatment dosing before blood draw will be entered in the eCRF.

The site staff will ship the plasma samples to the central laboratory. The central laboratory will ship the samples to the CRO in charge of the PK analysis (see page 3 for contact details).

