#### 8.2.4 Visit 6 – EOT

The EOT visit will take place at Week 12 ( $\pm$  5 days) or earlier in case of premature discontinuation of study treatment. In all cases, the EOT visit must preferably take place 1 day after the last dose of study treatment intake but no later than 7 days after the last dose of study treatment intake. The visit includes:

- SF-36v2™ questionnaire (to be completed prior to any other assessment)
- Recording of changes in concomitant medications and background SLE therapies since Visit 5
- Recording of methods of contraception (for WOCBP)
- Complete physical examination
- Body weight
- SLEDAI-2K and PGA
- SBP/DBP
- 12-lead ECG
- Echocardiography (under the responsibility of the echocardiography specialist)
- Spirometry (under the responsibility of the pulmonary function laboratory technician or expert)
- Ophthalmological examination (under the responsibility of the ophthalmologist)
- OCT (under the responsibility of the ophthalmologist)
- Hematology (including coagulation tests) and blood chemistry
- Urine pregnancy test (for WOCBP)
- ANA, anti-dsDNA antibodies, complement C3 and C4
- Exploratory biomarkers
- Lymphocyte subsets
- Urine protein-to-creatinine ratio
- Urinalysis
- PK sampling

- Study drug accountability
- Recording of AEs/SAEs
- Remind WOCBP to use the methods of contraception defined for this study
- Schedule an appointment for the next visit and instruct the subject to:
  - come fasted to the site
  - contact the principal investigator / treating physician immediately in the event of the appearance of any symptoms (e.g., suggestive of an SLE flare) or any AEs or SAEs or if a study treatment dose is missed.

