### 5.5.1 Main pharmacodynamic variable

The main variable is the change in lymphocyte count in peripheral blood from baseline to EOT, defined as:

- Total lymphocyte count at EOT – total lymphocyte count at baseline

The value at baseline is defined as the last non-missing value obtained from a sample taken prior to the first study treatment intake.

The value at EOT is defined last post-baseline value from a sample taken at least 21 days after the first study treatment intake (with no interruptions) and no later than 7 days after the last study treatment intake for the analyses on the PDS and on the PPS.

The value at EOT is defined as the last post-baseline value up to Week 12 for the analyses on the FAS (application of the intention-to-treat principle [ITT] utilizing the Last observation carried forward [LOCF] technique for missing data).

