***Population flags***

**Screened Subject Flag** is assigned to Y for all subjects who have a record in the DM domain.

**Re-Screened Subject Flag** is assigned to:

- Y for subjects who have a record in the SV domain with a visit number equal to 1.1
- N otherwise.

**Randomized Population Flag** is assigned to:

- Y for all subjects who have a record in DS domain with a Standardized Disposition Term equal to RANDOMIZED
- N otherwise.

**Full Analysis Set Population Flag** is assigned to:

- Y for all subjects who have a record in DS domain with a Standardized Disposition Term equal to RANDOMIZED
- N otherwise.

**Safety Analysis Set Population Flag** is assigned to

- Y for all subjects who have a record in EX domain corresponding to the first study treatment administration (Group ID =DAY 1 /RE-INITIATION)
- N otherwise.

**Per-protocol Population Flag** is assigned to:

- Y for all subjects included in the Full Analysis Set who have no record in the DV domain flagged as 'leading to exclusion from PPS'
- N otherwise.

**Pharmacokinetic Analysis Set Population Flag** is assigned to:

- Y for all subjects included in the Safety Analysis Set who have at least one non-missing ACT-33341 concentration available post-baseline
- N otherwise.

**Pharmacodynamic Analysis Set Population Flag** is assigned to:

- Y for all subjects:
  - included in the Safety Analysis Set,
  - with an available baseline value for lymphocyte count (from a sample taken from ICF through first study treatment),
  - with an available post-baseline value for lymphocyte count (from a sample taken at least 21 days after the first study treatment intake but no later than 7 days after the last study treatment without treatment interruption documented in the first 3 weeks).
- N otherwise.

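### SAP Table 15 replaces a missing last-dose date with the Visit 6 date, which by protocol lies 1 to 7 days after dosing ended; this overstates exposure and leaves the 7-day on-treatment limit unable to exclude a Visit 6 lymphocyte sample

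*SAP*

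**What the plan says.** **Imputation.** In the end-of-study-treatment row of SAP Table 15, a fully missing date becomes "Date of V6 - (Premature) End of Treatment". With the day missing, the rule takes the earlier of the last day of the month "and the Visit 6 (EOT) date". With day and month missing, it takes the earlier of 31 December and Visit 6.

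**Timing of Visit 6.** Protocol 8.2.4 says that "the EOT visit must preferably take place 1 day after the last dose of study treatment intake but no later than 7 days" after it. Protocol 3.1.1.2 sets the same interval.

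**Main endpoint.** SAP 5.5.1 takes the last lymphocyte value from a sample at least 21 days after first intake and "no later than 7 days after the last study treatment intake for the analyses on the PDS and on the PPS". The PDS flag in SAP 11.2.2 repeats the limit ("no later than 7 days after the last study treatment without treatment interruption documented in the first 3 weeks"), as does the extra end-of-treatment record (AVISITN 6.2) in SAP 11.1.1.

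**Visit windows.** SAP Table 11 assigns a sample to EOS if it is more than 105 days from first intake or more than 42 days from last intake. The Week 12 window is Days 71 to 105. The FAS end-of-treatment record (AVISITN 6.1) is the latest value assigned to Week 2 through Week 12.

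**PK.** For Week 12, SAP 10.11 and 11.2.20 keep "samples taken within 1 to 7 days following the last dose". Protocol 7.3.2 states: "The date and time of the last study treatment dosing before blood draw will be entered in the eCRF".

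SAP 11.2.1 allows analysis dates to be imputed. No section exempts imputed dates from these checks.

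**The concern.** Visit 6 is by design not a dosing day, so the imputed date is wrong even when the visit is on time. The SAP rewrote the PDS (section 4.1.1) so that the lymphocyte value would be one taken under treatment, and the 7-day limit is what enforces this at the end of dosing. For a subject whose off-drug time is unknown, the imputation sets that time to zero and the limit stops working. A recovering count could then stand as the on-treatment value and pull the dose effect toward zero. A better source, the last-dose date entered with the PK sample, is already collected, and Table 15 does not use it.

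**Working it through.** The plan gives no figure for this point, so the check follows the dates. Let g be the true number of days from last dose to Visit 6. It is assumed that the Table 15 date feeds the last-exposure date used in the visit and PDS rules.

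**1. Fully missing date, sample on the Visit 6 date.** Computed gap = Visit 6 date − Visit 6 date = 0, whatever g is.

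| True gap g | 7-day limit, true date | 7-day limit, imputed date | Duration overstated by |
|---|---|---|---|
| 1–7 days | met | met | 1–7 days |
| 8–14 days | not met | met | 8–14 days |

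The lymphocyte classification changes only in the second row. Duration is wrong in both, because SAP 11.2.5.1 computes it as last date minus first date plus 1.

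**2. Only the day missing.** The computed gap is 0 whenever Visit 6 falls in the same calendar month as the last dose. Over all last-dose dates in a 365-day year, that share is 1 − 12g/365:
- g = 1: 1 − 12/365 = 96.7%.
- g = 7: 1 − 84/365 = 77.0%.
- Average over g = 1 to 7 (mean 4): 1 − 48/365 = 86.8%.

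A visit more than 7 days after the last dose is still caught in a share 12(g − 7)/365: 12/365 = 3.3% at g = 8 and 84/365 = 23.0% at g = 14.

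**3. The 42-day EOS rule.** Illustration: last dose on Day 40, Visit 6 on Day 47 (g = 7, on time), EOS sample on Day 84.
- True date: 84 − 40 = 44, which is more than 42, so the sample is EOS.
- Imputed date: 84 − 47 = 37, which is not more than 42, so the sample falls in the Week 12 window (71–105). As the latest value there, it becomes the FAS end-of-treatment value, six weeks off drug.

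This needs no late visit, only early discontinuation. It does not reach the PDS, where 37 days still exceeds 7. A sample 42 days or fewer after the last dose would escape the EOS rule even with the true date, so only samples beyond 42 days are attributable to the imputation.

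**4. Size per affected subject.** Protocol 11.6.1 plans a baseline of 2.0 and a maximum reduction of 70%, so the maximum change is 0.7 × 2.0 = 1.4 x10^9/L. With 12 per arm and 10% excluded, about 0.9 × 12 = 10.8, or 11, remain.
- Count recovered to 1.0 (change −1.0): (1.4 − 1.0)/11 = 0.036 x10^9/L, and 0.036/1.4 = 2.6% of the maximum effect.
- Full recovery to baseline (change 0): 1.4/11 = 0.127 x10^9/L, and 0.127/1.4 = 9.1%.

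The first case matches Phase 1, where protocol 1.3.2.2 defines recovery as a mean of at least 1.0 x10^9/L, reached at 28 days after 4 mg. The second is an upper limit.

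**5. PK.** SAP 11.2.20 uses one definition of days since last dose for Visits 3 to 7. At Visits 3 to 5 dosing continues, so the last dose there can only be the one before that draw, which protocol 7.3.2 records. If the same source serves Visit 6, the imputation does not touch the PK rule. If the imputed date were used, a Visit 6 sample would be at day 0 and fail the 1-to-7-day rule. The SAP does not name the source.

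**The case against.** **Two conditions must coincide for the PDS.** For on-time visits the 7-day limit is met with either date. The main analysis changes only if the date is missing and Visit 6 came more than 7 days after the last dose, against protocol. This stands and limits the point.

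**The FAS analysis is a safeguard.** SAP 10.6.4 repeats MCP-Mod and ANCOVA on the FAS, without a 7-day limit. Protocol 11.2.3 also accepts FAS data after treatment stops, so an off-drug value there is not wrong in itself. This stands in part: the FAS value still depends on the imputed date through the 42-day rule, which the SAP wrote to send such samples to EOS.

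**The dates may never be missing.** The Study Drug Log captures the end of treatment. This also stands; no frequency is given.

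Three stronger readings are tempting, and the documents do not support them:
- *The Week 12 PK value is always lost.* This requires the PK rule to use the imputed date, and the wording for Visits 3 to 7 points the other way.
- *The 7-day limit is always met.* A sample drawn 8 or more days after Visit 6 still fails, and a date with only the day missing does not always give a gap of 0.
- *Compliance is pushed below the 80% deviation limit.* A longer duration does lower the recomputed figure in SAP 5.3.2; for example, 67/80 = 83.8% becomes 67/87 = 77.0% with 7 extra days. But the deviation in protocol 5.1.7.2 uses days between visits, and the eCRF figure uses visit dates. The recomputed figure is only summarised (SAP 10.5.2). The list of deviations that exclude a subject from the PPS is not visible, so an effect there cannot be shown.

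**Conclusion.** The inconsistency is real. A missing last-dose date is replaced by a date on which, under the protocol, dosing has already ended. For each affected subject, duration is overstated by the true gap (1 to 7 days if the visit is on time). The 7-day limit cannot exclude a Visit 6 sample when the date is fully missing, and seldom does so for a slightly late visit when only the day is missing. After early discontinuation, an off-drug sample can become the FAS end-of-treatment value.

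The effect on the main result is small and conditional: about 0.04 x10^9/L on an arm mean per misclassified subject with the count at 1.0 x10^9/L, and at most 0.13 x10^9/L under full recovery. Both assume about 11 subjects in the arm and the planned maximum effect of 1.4 x10^9/L, which not every dose arm need reach. A visit only a few days late would shift the mean less, since the multiple-dose half-life is 12 to 22 days (protocol 1.3.2.1). With no missing dates the effect is zero. Loss of the Week 12 PK value is a possibility left open by an unnamed date source, not a demonstrated consequence.

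**What to change.** - **Table 15:** impute the end of study treatment first from the last-dose date and time entered in the eCRF with the Visit 6 PK sample, or with the Visit 7 sample if Visit 6 is missing. Use the Visit 6 date minus 1 day, the protocol's preferred interval, only if neither exists.
- **SAP 11.2.20 (and 10.11):** state that the PK timing rule uses the recorded last-dose date.
- **SAP 10.6.4:** add a sensitivity analysis of the main PD endpoint. For subjects whose last-dose date was imputed, do not count the Visit 6 sample as on treatment; use the latest earlier qualifying sample. This is needed because the minus-1-day fallback still cannot detect a late visit.

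Requiring a recorded last-dose date for PDS membership would go too far: it could remove subjects with valid Week 4 or Week 8 samples taken during continued dosing.

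The cost is one table row, a cross-reference and one extra analysis. No new data are needed.

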## 15 APPENDICES

### 15.1 Protocol Synopsis

A.

|            |   |
|------------|---|
| TITLE      | A multicenter, randomized, double-blind, placebo-controlled, dose-response study to investigate the biological activity, safety, tolerability, and pharmacokinetics of ACT-334441 in subjects with systemic lupus erythematosus.  |
| OBJECTIVES | 
Main objectives
 

• To investigate the pharmacodynamics (PD) of ACT-334441 in adult subjects with systemic lupus erythematosus (SLE).

• To investigate the safety and tolerability of ACT-334441 in adult subjects with SLE.

 
Exploratory objectives
 

• To investigate the pharmacokinetics (PK) of ACT-334441 in adult subjects with SLE.

• To investigate the effect of ACT-334441 treatment on disease activity in adult subjects with SLE.

  |
| DESIGN     | 
Prospective, multicenter, multinational, randomized, double-blind, placebo-controlled, two-part, dose-response Phase 1/2 study.
 
This study is divided in two parts:
 

• Part A: Four parallel treatment groups (including 0.5 mg, 1 mg, or 2 mg of ACT-334441 and placebo control).

 
An interim safety review will be conducted by the Independent Data Monitoring Committee (IDMC) when all subjects enrolled into Part A have completed Visit 4, unless prematurely discontinued. The IDMC will then evaluate the safety profile of ACT-334441 in SLE patients and give a recommendation whether or not to continue the study as planned (i.e., proceed to Part B).
 

• Part B: Two parallel treatment groups (including 4 mg ACT-334441 and placebo control).

 
Note: Subjects enrolled in Part A are not eligible to participate
 |

|   |   |
|---|---|
| PERIODS   | 
in Part B.
 
There will be three periods in Part A and Part B.
 
Screening period:
 
This period starts up to 30 days before randomization and includes the Screening visit and the pre-randomization assessments.
 
Treatment period:
 
The treatment period will last 12 weeks. Visits during the treatment period will consist of a Randomization visit and visits at Weeks 2, 4, 8, and 12.
 
The End-of-Treatment (EOT) visit will take place at Week 12, or earlier in case of premature discontinuation of study treatment. In all cases, the EOT visit should take place 1 day after the last dose of study treatment but no later than 7 days after the last dose of study treatment.
 
Follow-up period:
 
Subjects will undergo an End-of-Study (EOS) Visit 6 weeks after the last dose of study treatment.
 
Follow-up assessments via telephone calls will be performed 11 weeks and 16 weeks after the last dose of study treatment to evaluate potential serious adverse events (SAEs) and to assess pregnancy status (urine test).
 |
| STUDY DISCONTINUATION CRITERIA AND STUDY-SPECIFIC CRITERIA FOR INTERRUPTION / CLINICAL STUDY STOP | 
Study treatment discontinuation
 
At any time during the double-blind treatment period, subjects meeting the study-specific criteria for permanent discontinuation of study treatment as described in Sections 5.1.9 and 5.1.10 are to be permanently discontinued from study treatment and will perform EOT and EOS visits and will be followed up for a total of 16 weeks after last study treatment intake (telephone calls follow-up for pregnancy and SAEs).
 
Study-specific criteria for interruption / stopping of the clinical study or Part B
 

Part A: if 12 or more subjects out of the planned 36 subjects in the combined active treatment groups (0.5, 1, or 2 mg) or 6 or more subjects out of the planned 12 subjects in the high dose group (2 mg) have been discontinued study treatment due to meeting any of the

   |

|                           |   |
|---------------------------|---|
|                           | 
individual patient's stopping rules as defined per safety area of interest [see Section 9.3], the entire study will be put on hold. A detailed safety signal assessment and recommendations from IDMC and Health Authorities may allow a potential restart of the study.
 

Part B: if 4 or more subjects out of the planned 12 subjects in the active treatment group (4 mg) have been discontinued study treatment due to meeting any of the individual patient's stopping rules as defined per safety area of interest [see Section 9.3], all subjects included in Part B will stop study treatment. A detailed safety signal assessment and recommendations from IDMC and Health Authorities may allow a potential restart of the Part B.

 |
| PLANNED DURATION          | 
Part A: Approximately 11 months from First subject-First visit (FSFV) to Last Subject-Last Visit (LSLV).
 
Part A and B: Approximately 20 months from FSFV to LSLV.
   |
| SITE(S)
/ COUNTRY(IES) | Approximately 21 sites notably in the USA, Russia and Europe.   |
| SUBJECTS / GROUPS         | 
Part A: Approximately 48 subjects will be randomized (1:1:1:1) via an interactive response technology (IRT) system to one of four groups (i.e., 12 subjects in each group; three dose levels of 0.5 mg, 1 mg, or 2 mg ACT-334441, or placebo once daily [o.d.]).
 
Part B: Approximately 16 subjects will be randomized (3:1) via an IRT system to one of two groups (i.e., 12 subjects receiving 4 mg ACT-334441 and 4 receiving placebo o.d.).
  |
| INCLUSION CRITERIA        | 

1. Signed informed consent prior to initiation of any study-mandated procedure.

2. Men or women <math>\geq 18</math> and <math>\leq 65</math> years of age.

3. Women of childbearing potential as defined in Section 4.5.1:

• must have a negative serum pregnancy test at Screening and a negative urine pregnancy test at Randomization at least 3 weeks apart;

• must agree to undertake a urine pregnancy test as indicated in Table 1 (bi-weekly/ monthly) during

   |

|                    |  |
|--------------------|--|
|                    | 
the study and up to 16 weeks after study treatment discontinuation;
 

• must use methods of contraception, as described in Section 4.5.2, from the Screening visit until 16 weeks after study treatment discontinuation.

 
4. Presenting with a diagnosis of SLE made at least 6 months prior to Screening, by fulfilling at least 4 of the 11 criteria for SLE, as defined by the American College of Rheumatology (criteria are cumulative and do not need to be present concurrently) [Tan 1982; Hochberg 1997].
 
5. Presenting with a Systemic Lupus Erythematosus Disease Activity Index-2000 (SLEDAI-2K) score of at least 2 points for musculoskeletal or mucocutaneous manifestations (i.e., myositis, arthritis, rash, alopecia, mucosal ulcers) at Screening.
 
6. History or presence at Screening of positive anti-nuclear antibodies (ANA) or anti-double-stranded DNA (anti-dsDNA) antibodies.
 
7. Currently treated for at least 30 days prior to Randomization with stable doses of one or more of the following background medications:
 

• Non-steroidal anti-inflammatory drugs (NSAIDs),

• Corticosteroids (<math>\leq 10</math> mg/day prednisolone or equivalent),

• Anti-malarials (<math>\leq 400</math> mg/day hydroxychloroquine, <math>\leq 500</math> mg/day chloroquine, <math>\leq 100</math> mg/day quinacrine)#,

• Mycophenolate mofetil (<math>\leq 2</math> g/day)#,

• Azathioprine (<math>\leq 2</math> mg/kg/day)#,

• Methotrexate (<math>\leq 20</math> mg/week)#.

 
#Treatment with anti-malarials, mycophenolate mofetil, azathioprine, or methotrexate must have been started at least 90 days prior to Randomization and must not have been stopped within 30 days prior to Randomization.
 |
| EXCLUSION CRITERIA | 
Pregnancy and breastfeeding
 

1. Breastfeeding, pregnant women or women planning to become pregnant during the study.

 
SLE disease
 

2. Subjects with active lupus nephritis (defined by proteinuria <math>> 1</math> g/24 h, or equivalent using spot urine

   |

|  |   |
|--|---|
|  | 
protein-to-creatinine ratio) within 90 days prior to randomization; subjects with central nervous system lupus (e.g., aseptic meningitis, seizures, cerebritis, polyneuropathy, cerebrovascular disease) within 90 days prior to Randomization; subjects with lupus vasculitis within 90 days prior to Randomization.
 
3. Subjects presenting with a SLEDAI-2K score > 12 at Screening or at Randomization.
 
Cardiovascular
 

4. History or presence of cardiac rhythm disorders (e.g., sinoatrial heart block, second- or third-degree atrioventricular block, symptomatic bradycardia, atrial flutter or atrial fibrillation, ventricular arrhythmias, cardiac arrest).

5. Resting heart rate (HR) < 55 bpm as measured by the pre-dose 12-lead electrocardiogram (ECG) on Day 1; an increased QT corrected for HR on the basis of Fridericia's formula (QTcF) interval of > 470 ms (females), > 450 ms (males) at Screening, or on Day 1 ECG prior to study treatment initiation.

6. History or presence of ischemic heart disease.

7. History or presence of myocarditis or endocarditis.

8. Presence of valvular heart disease associated with symptoms or hemodynamic change.

9. History of syncope associated with cardiac disorders.

10. History or presence of cardiac failure.

11. Systemic arterial hypertension not controlled by medication according to investigator judgment.

12. History or presence of vascular thrombosis at any time or a history of pregnancy morbidity in the context of anti-phospholipid antibody syndrome within 5 years prior to Randomization.

13. Clinically relevant hypotension according to investigator's judgment or orthostatic hypotension (i.e., > 20 mmHg decrease in systolic blood pressure [SBP] or > 10 mmHg decrease in diastolic blood pressure [DBP] from supine to standing position measured between 1 and 3 minutes after standing) at Screening.

14. Known pulmonary arterial hypertension of functional class III or IV.

 
Pulmonary
 

15. History or presence of severe respiratory disease or

 |
|--|---|

|  |  |
|--|--|
|  | 
pulmonary fibrosis, based on medical history, lung function and chest X-ray (CXR) performed at Screening or within 3 months prior to Screening.
 
16. Bronchial asthma or chronic obstructive pulmonary disease.
 
17. Abnormal pulmonary function tests: forced expiratory volume in 1 second (FEV1) or forced vital capacity (FVC) < 70% of predicted normal value; FEV1/FVC ratio <0.7.
 
Treatments
 
18. Treatment or planned treatment with the following medications*:
 

Within 15 days or 5 half-lives of the medication, whichever is longer, prior to Randomization:

β-blockers, diltiazem, verapamil, digoxin or any other anti-arrhythmic or HR-lowering systemic therapy (list of drugs provided in Appendix 1).

QT-prolonging drugs with known risk of torsades de pointes, for any indication (list of drugs provided in Appendix 2).

Short- and long-acting β2-agonists (e.g., albuterol, levalbuterol, formoterol, terbutaline salmeterol).

Within 30 days or 5 half-lives of the medication, whichever is longer, prior to Randomization:

Cyclophosphamide, cyclosporine, tacrolimus, sirolimus, etc.,

Pulse methylprednisolone

Vaccination with live vaccines.

Within 90 days prior to Randomization:

Belimumab, leflunomide,

Any investigational immunosuppressive or immunomodulatory agent (within 90 days or 5 half-lives of the drug prior to start of study treatment, whichever is longer).

Within 12 months prior to Randomization:

B cell-depleting biological agents such as rituximab or ocrelizumab.

Any time prior to Randomization:

Alemtuzumab, sphingosine-1-phosphate (S1P) modulators (e.g., fingolimod).

 |
|--|--|

|  |   |
|--|---|
|  | 
*For immunosuppressants or anti-inflammatory drugs not listed among the forbidden medications, the investigator should discuss adequate wash-out time with the sponsor.
 
Infection and infection risk
 
19. Active or latent tuberculosis (TB), as assessed by CXR performed at Screening or within 3 months prior to Screening, and interferon gamma release assay (QuantiFERON-TB-Gold®) at Screening, except if there is documentation that the subject has completed adequate and successful treatment for latent TB infection or TB disease previously.
 
20. Ongoing known bacterial, viral or fungal infection that is of clinical concern in the judgment of the investigator.
 
21. A history of any serious infection, defined as life-threatening or requiring intravenous (i.v.) antibiotics or hospitalization, within 30 days prior to Randomization.
 
22. Hepatitis B and C, congenital or acquired severe immunodeficiency or known human immunodeficiency virus (HIV) infection or positive HIV testing at Screening.
 
23. Negative antibody test for varicella-zoster virus at Screening.
 
Malignancy
 
24. History or presence of malignancy (except for surgically excised basal or squamous cell skin lesions), lymphoproliferative disease, or history of total lymphoid irradiation.
 
Transplantation
 
25. History or presence of bone marrow or solid organ transplantation.
 
Ophthalmology
 
26. Presence of macular edema or active uveitis.
 
Metabolic and hepatic
 
27. Type 1 or 2 diabetes that is poorly controlled according to investigator judgment, or diabetes complicated with organ involvement such as diabetic nephropathy or retinopathy.
 
28. Moderate or severe hepatic impairment defined as Child Pugh Score B or C, respectively, based on measurement of total bilirubin (TBL), serum albumin, international normalized ratio, as well as on presence/absence and severity of ascites and hepatic encephalopathy.
 
29. TBL > 1.5-fold upper limit of normal (ULN; unless in the context of known Gilbert's Syndrome).
 |
|--|---|

|                  |  |
|------------------|--|
|                  | 
30. Alanine aminotransferase (ALT) or aspartate aminotransferase (AST) > 2-fold ULN.
 
Hematology
 
31. Hemoglobin < 9 g/dL.
 
32. White blood cell count < 2500/<math>\mu</math>L (<math>2.5 \times 10^9</math>/L).
 
33. Lymphocyte count < 800 /<math>\mu</math>L (<math>0.8 \times 10^9</math>/L).
 
34. Platelets < 75,000/<math>\mu</math>L (<math>75 \times 10^9</math>/L).
 
Renal
 
35. Proteinuria > 1.0 g/24 hour or equivalent using spot urine protein-to-creatinine ratio.
 
36. Estimated glomerular filtration rate < 60 mL/min/1.73 m^2.
 
Other categories
 
37. History of clinically significant drug or alcohol abuse.
 
38. Known allergy to S1P receptor 1 modulators or any of the ACT-334441 formulation excipients.
 
39. Any other clinically relevant medical or surgical condition that in the opinion of the investigator would put the subject at risk if participating in the study.
 
40. Subjects unlikely to comply with protocol, e.g., uncooperative attitude, inability to return for follow-up visits or likelihood of not completing the study, including mental condition rendering the subject unable to understand the nature, scope, and possible consequences of the study.
 |
| STUDY TREATMENTS | 
Investigational treatment
 
ACT-334441 0.5 mg, 1 mg, 2 mg capsules for Part A, and 4 mg capsules for Part B, administered orally o.d. in the morning.
 
Placebo
 
Placebo matching ACT-334441 capsules administered orally o.d. in the morning.
  |

|                     |  |
|---------------------|--|
| CONCOMITANT THERAPY | 
Allowed concomitant therapy
 

• i.v. atropine in the event of symptomatic bradycardia [see study-specific criteria for permanent discontinuation of study treatment in Section 5.1.10];

• Dilating eye drops, mydriatics, including parasympathetic antagonists (e.g., tropicamide) or sympathetic agonists (e.g., phenylephrine) for topical use;

• Vaccination with non-live vaccines;

• Stable systemic corticosteroid therapy; corticosteroids are not to be started or stopped during the study, and the dose should be kept stable. However, the investigator may see reason to initiate or increase the dose of systemic corticosteroid to treat an SLE flare or another condition. In such cases, the dose may be increased for a period of not more than 14 days up to double the baseline dose or a maximum of 20 mg/day prednisolone or equivalent (please refer to conversion table in Appendix 8);

• Topical treatment therapy including topical use of corticosteroid;

• Stable antimalarial therapy (e.g., hydroxychloroquine, chloroquine, quinacrine); therapy is not to be started or stopped during the study, and dose should be kept stable;

• Stable NSAID chronic therapy. Therapy is not to be started or stopped during the study;

– Temporary use and/or dose change for treatment of non-SLE-related conditions (e.g., headache, menstrual cramps) is allowed;

• Stable immunosuppressant therapy (i.e., methotrexate, azathioprine, or mycophenolate mofetil). Therapy is not to be started or stopped during the study, and dose should be kept stable.

 
Forbidden concomitant medication
 

• Immunosuppressives not listed in allowed concomitant medication such as cyclophosphamide, cyclosporine,

 |
|---------------------|--|

|           |  |
|-----------|--|
|           | 
leflunomide, sirolimus, tacrolimus, etc.;
 

• Immunosuppressive or immunomodulatory biological agents (e.g., belimumab, i.v. immunoglobulin, rituximab, S1P modulators other than ACT-334441);

• <math>\beta</math>-blockers, diltiazem, verapamil, digoxin, or any other anti-arrhythmic or HR-lowering therapy (as listed in Appendix 1);

• QT-prolonging drugs with known risk of torsades de pointes (list of drugs provided in Appendix 2);

• Short- and long-acting <math>\beta_2</math>-agonists (e.g., albuterol, levalbuterol, formoterol, terbutaline salmeterol);

• Vaccination with live vaccines.

  |
| ENDPOINTS | 
Pharmacodynamic endpoints
 

• Change in total lymphocyte count from baseline to EOT

• Change in total lymphocyte count from baseline to each post-baseline assessment

 
Safety endpoints
 
The treatment-emergent period is defined as the time from first study treatment intake up to 6 weeks (inclusive) after last study treatment intake.
 

• Treatment-emergent adverse events (AEs), SAEs, and adverse events of special interest (AESI#);

• AEs leading to premature discontinuation of study treatment;

• Changes in 12-lead ECG variables (HR, PR, QRS, QT, QT corrected for HR on the basis of Bazzett's formula [QTcB] and QT corrected for HR on the basis of Fridericia's formula [QTcF]), from pre-dose to selected post-dose assessments (1 h, 2 h, 3 h, 4 h, 5 h, 6 h) on Day 1 and on day of study drug re-initiation;

• Occurrence of treatment-emergent 12-lead ECG outliers (e.g., HR, PR, QTc defined in the Statistical Analysis Plan [SAP]);

• Occurrence of treatment-emergent 12-lead ECG abnormalities;

• Occurrence of treatment-emergent ECG-Holter

 |

|  |  |
|--|--|
